6.3.2 Treatment assignment, randomization

No randomization will be performed in this study. All eligible patients will receive eltrombopag per the treatment schedule.

6.4 Treatment blinding

Not applicable.

[REDACTED]

6.5 Dose escalation and dose modification

6.5.1 Dose escalation guidelines

Dose escalation will be allowed from 50 mg QD to 75 mg QD as described in [Section 6.1](#).

Patients will be treated with eltrombopag 50 mg QD for 2 weeks to reach a target platelet count of $\geq 100 \times 10^9/L$ (CR). For those patients who do not achieve the target platelet count within 2 weeks, the dose of eltrombopag will be increased to 75 mg QD.

6.5.1.1 Starting dose

In this study, the starting dose will be 50 mg eltrombopag QD (starting dose for Asian patients will be 25 mg QD, reduced as per [Section 6.1](#)).

This eltrombopag starting dose is consistent with the dosing guidelines that have been approved for eltrombopag use in adult patients with chronic ITP.

6.5.2 Dose modifications

For patients who do not tolerate the protocol-specified dosing schedule, dose interruptions and/or reductions are either recommended or mandated in order to allow patients to continue the study treatment.

These dose modifications are summarized in [Table 6-3](#). Deviations to mandatory dose interruptions and/or reductions are not allowed. Permanent treatment discontinuation is mandatory for specific events indicated as such in [Table 6-4](#).

Table 6-3 Eltrombopag Dose Adjustments in ITP

Platelet count	Dose adjustment or response
< $100 \times 10^9/L$ following 2 weeks of therapy	Increase daily dose by 25 mg to a maximum of 75 mg/day ^a
$\geq 100 \times 10^9/L$ to $< 200 \times 10^9/L$	Use lowest dose of eltrombopag to maintain platelet counts around $100 \times 10^9/L$ for 2 months prior to per protocol tapering ^a
$\geq 200 \times 10^9/L$ to $\leq 400 \times 10^9/L$	Decrease daily dose by 25 mg. Wait 2 weeks to assess the effects of this and any subsequent dose adjustments ^{b c}
$> 400 \times 10^9/L$	Stop eltrombopag; increase the frequency of platelet monitoring to twice weekly. Once the platelet count is $< 150 \times 10^9/L$, reinitiate therapy at a lower daily dose ^{b c}

a. This dose adjustment schedule was chosen for this study to have patients use the minimal efficacious dosage of eltrombopag in order to achieve a CR. Patients need to maintain a CR for a minimum of 2 months before tapering off can be attempted.

b. For patients taking eltrombopag once daily, consideration should be given to dosing at 12.5 mg once daily or alternatively a dose of 25 mg once every other day

c. Source: The latest version of the eltrombopag core data sheet (CDS).

These dose changes must be recorded on the appropriate CRF.

Eltrombopag can cause hepatobiliary laboratory abnormalities, severe hepatotoxicity, and potentially fatal liver injury. Serum ALT, AST and bilirubin should be measured prior to initiation of eltrombopag, every 2 weeks during the dose adjustment phase and monthly after establishment of a stable dose. Abnormal serum liver tests should be evaluated with repeat

testing within 3 to 5 days. If the abnormalities are confirmed, serum liver tests should be monitored weekly until the abnormalities resolve, stabilize, or return to baseline levels.

For the grading of adverse events and laboratory results, the Common Terminology Criteria for Adverse Events (CTCAE) Version 4.03 will be used.

Table 6-4 Criteria for dose adjustment based on liver enzyme and bilirubin levels

Dose modifications for ETB115	
Worst toxicity CTCAE^a Grade (value) during the treatment	Investigations (Hepatic)
Isolated Total Bilirubin Elevation	
> ULN – 1.5 x ULN	Maintain dose level
> 1.5 - 3.0 x ULN*	Interrupt dosing and weekly monitor liver function tests (LFTs) ^b , or more frequently if clinically indicated, until resolved to $\leq 1.5 \times$ ULN: If resolved in ≤ 14 days, then resume at same dose level If resolved in > 14 days, then decrease one dose level ^e
> 3.0 - 10.0 x ULN**	Mandatory: Interrupt dosing and weekly monitor LFTs ^b , or more frequently if clinically indicated, until resolved to $\leq 1.5 \times$ ULN: If resolved in ≤ 14 days, then decrease one dose level ^e If resolved in > 14 days, then discontinue patient from study drug treatment. LFTs ^b will continue to be monitored weekly, or more frequently if clinically indicated, until total bilirubin have resolved to baseline or stabilization over 4 weeks.
> 10.0 x ULN	Mandatory: Discontinue patient from study drug treatment The patient should be monitored weekly (including LFTs ^b), or more frequently if clinically indicated, until total bilirubin have resolved to baseline or stabilization over 4 weeks.
	* Note: If total bilirubin $> 1.5 - \leq 3 \times$ ULN is due to the indirect (non-conjugated) component only, no changes to dose are required. ** Note: If total bilirubin $> 3.0 - 10.0 \times$ ULN is due to the indirect (non-conjugated) component only, and hemolysis as the etiology has been ruled out as per institutional guidelines (e.g., review of peripheral blood smear and haptoglobin determination), then decrease 1 dose level ^e and continue treatment at the discretion of the investigator
Isolated AST or ALT elevation	
> ULN - 3.0 x ULN	Maintain dose level
> 3.0 - 5.0 x ULN	Maintain dose level. Repeat LFTs ^b as soon as possible, preferably within 48-72 hours from awareness of the abnormal results. If abnormal lab values are confirmed upon the repeat test, then monitor LFTs ^b weekly, or more frequently if clinically indicated, until resolved to $\leq 3.0 \times$ ULN Discontinue patient from the study drug treatment if elevation is combined with any of the following: Clinical symptoms of liver injury or evidence for hepatic decompensation

Dose modifications for ETB115	
Worst toxicity CTCAE^a Grade (value) during the treatment	Investigations (Hepatic)
	Progressively increasing LFTs ^b upon repeat testing Persistence ≥ 4 weeks
> 5.0 - 10.0 x ULN	Mandatory: Interrupt dose. Repeat LFTs ^b as soon as possible; preferably within 48-72 hours from awareness of the abnormal results. Monitor LFTs ^b weekly, or more frequently if clinically indicated until resolved to $\leq 3.0 \times$ ULN then: If resolved in ≤ 14 days, maintain dose level If resolved > 14 days, decrease one dose level ^e Mandatory: Interrupt dose. Repeat LFTs ^b as soon as possible, preferably within 48-72 hours from awareness of the abnormal results. Monitor LFTs ^b weekly, or more frequently if clinically indicated until resolved to \leq baseline. Then decrease one dose level ^e
> 10.0 - 20.0 x ULN	Mandatory: Discontinue patient from study drug treatment Repeat LFTs ^b as soon as possible, preferably within 48-72 hours from awareness of the abnormal results. Monitor LFTs ^b weekly, or more frequently if clinically indicated until resolved to \leq baseline or stabilization over 4 weeks..
Combined^c elevations of AST or ALT and total bilirubin	
For patients with normal baseline ALT and AST and total bilirubin value [AST or ALT $> 3.0 \times$ ULN] combined with [total bilirubin $> 2.0 \times$ ULN] without evidence of cholestasis ^d OR For patients with elevated baseline AST or ALT [AST or ALT $> 3 \times$ baseline] OR [AST or ALT $> 5.0 \times$ ULN], whichever is lower, combined with [total bilirubin $> 2 \times$ baseline AND $> 2.0 \times$ ULN]	Mandatory: Permanently discontinue patients from study drug treatment. Repeat as soon as possible, preferably within 48 hours from awareness of the abnormal results, then with weekly monitoring of LFTs ^b), or more frequently if clinically indicated, until AST, ALT, or bilirubin have resolved to baseline or stabilization over 4 weeks
All dose modifications should be based on the worst preceding toxicity. ^a Common Toxicity Criteria for Adverse Events (CTCAE Version 4.03) ^b Core LFTs consist of ALT, AST, GGT, total bilirubin (fractionated [direct and indirect], if total bilirubin $> 2.0 \times$ ULN), and alkaline phosphatase (fractionated [quantification of isoforms], if alkaline phosphatase $> 2.0 \times$ ULN.) ^c "Combined" defined as total bilirubin increase to the defined threshold concurrently with ALT/AST increase to the defined threshold If combined elevations of AST or ALT and total bilirubin do not meet the defined thresholds, please follow the instructions for isolated elevation of total bilirubin and isolated elevation of AST/ALT, and take a conservative	

Dose modifications for ETB115	
Worst toxicity CTCAE^a Grade (value) during the treatment	Investigations (Hepatic)
	
action based on the degree of the elevations (e.g. discontinue treatment at the situation when omit dose is needed for one parameter and discontinue treatment is required for another parameter). After all elevations resolve to the defined thresholds that allow treatment re-initiation, re-start the treatment either at the same dose or at one dose lower if meeting a criterion for dose reduction
 
^d "Cholestasis" defined as alkaline phosphatase (ALP) elevation ($>2.0 \times \text{ULN}$ and $R \text{ value } < 2$) in patients without bone metastasis, or elevation of ALP liver fraction in patients with bone metastasis
 
The R value is calculated by dividing the ALT by the ALP, using multiples of the ULN for both values. It denotes whether the relative pattern of ALT and/or ALP elevation is due to cholestatic ($R \leq 2$), hepatocellular ($R \geq 5$), or mixed ($R > 2$ and < 5) liver injury.
 
^e "One dose level" defined as eltrombopag dose reduction by 25 mg.

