6.5.3.2 Follow up on potential drug-induced liver injury (DILI) cases

Patients with transaminase increase combined with total bilirubin (TBIL) increase may be indicative of potential DILI, and should be considered as clinically important events.

The threshold for potential DILI may depend on the patient's baseline AST/ALT and TBIL value; patients meeting any of the following criteria will require further follow-up as outlined below:

- For patients with normal baseline ALT and AST: AST or ALT $> 3.0 \times$ ULN combined with TBIL $> 2.0 \times$ ULN OR INR > 1.5 without evidence of cholestasis (no ALP elevation)
- For patients with elevated AST or ALT or TBIL value at baseline: [AST or ALT $> 2 \times$ baseline AND $> 3.0 \times$ ULN] OR [AST or ALT $> 8.0 \times$ ULN], combined with [TBIL $> 2 \times$ baseline AND $> 2.0 \times$ ULN]
- For patients with normal baseline ALT: ALT $\geq 5 \times$ Upper Limit of Normal (ULN)

Medical review needs to ensure that liver test elevations are not caused by cholestasis, defined as Alkaline Phosphatase (ALP) elevation $> 2.0 \times$ ULN with R value < 2 in patients without bone metastasis, or elevation of ALP liver fraction in patients with bone metastasis.

Note: (The R value is calculated by dividing the ALT by the ALP, using multiples of the ULN for both values. It denotes whether the relative pattern of ALT and/or ALP elevation is due to cholestatic (R ≤ 2), hepatocellular (R ≥ 5), or mixed (R > 2 and < 5) liver injury).

These patients should be immediately discontinued from eltrombopag, and repeat liver function test (LFT) testing as soon as possible, preferably within 48 hours from the awareness of the abnormal results, then with weekly monitoring of LFTs), or more frequently if clinically indicated, until AST, ALT, or bilirubin have resolved to baseline or stabilization over 4 weeks. The evaluation should include laboratory tests, detailed history, physical assessment and the possibility of liver metastasis or new liver lesions, obstructions/compressions, etc.

1. Laboratory tests should include ALT, AST, albumin, creatinine kinase, TBIL, direct and indirect bilirubin, gamma-glutamyl-transferase (GGT), prothrombin time (PT)/ International Normalized Ratio (INR) and ALP.

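### For a baseline ALT/AST between 1 and 2.5 x ULN, Section 6.5.3.2 stops eltrombopag at combined liver results that Table 6-4 lets sites interrupt and restart, and no text ranks the two rules

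*Protocol*

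**What the plan says.** Section 5.2 (exclusion criteria 8 to 10) admits patients with ALT or AST up to 3.0 x ULN and bilirubin up to 1.5 x ULN, so a raised baseline is allowed.

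Two places in the protocol then set a stopping limit for a combined rise in transaminases and bilirubin when baseline transaminases are raised.

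- **Table 6-4 (Section 6.5.2), combined row.** The limb is headed "For patients with elevated baseline AST or ALT". The enzyme limit is "AST or ALT $> 3 \times$ baseline] OR [AST or ALT $> 5.0 \times$ ULN], whichever is lower", with bilirubin above both 2 x baseline and 2.0 x ULN. The action is mandatory permanent discontinuation. Footnote c covers combined elevations under these limits: if they "do not meet the defined thresholds, please follow the instructions for isolated elevation of total bilirubin and isolated elevation of AST/ALT", taking conservative action according to the degree of elevation. Once everything has resolved to the thresholds that permit re-initiation, sites are to "re-start the treatment either at the same dose or at one dose lower if meeting a criterion for dose reduction".
- **Section 6.5.3.2.** It opens with "patients meeting any of the following criteria will require further follow-up as outlined below". The relevant bullet begins "For patients with elevated AST or ALT or TBIL value at baseline". Its enzyme limit is "AST or ALT $> 2 \times$ baseline AND $> 3.0 \times$ ULN] OR [AST or ALT $> 8.0 \times$ ULN", with the same bilirubin condition. Medical review must make sure that cholestasis (ALP above 2.0 x ULN with R below 2) is not the cause. The action is "These patients should be immediately discontinued from eltrombopag".

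The Glossary defines treatment discontinuation as a permanent stop and interruption as a temporary one.

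Section 6.5.2 points to Table 6-4 for mandatory permanent discontinuation. Section 10.2.1 points to Table 6-4 and, if appropriate, to the general section on discontinuing treatment. Neither mentions Section 6.5.3.2.

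**The concern.** The two rules share a population, a bilirubin condition and a purpose, but not an enzyme limit. A site with a result between the limits finds an instruction to stop for good in one section. In the other it finds a route to interrupt and rechallenge. The cross-references lead to the table, which is the more permissive rule over most of the eligible range of raised baselines.

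This is first a safety matter. Section 6.5.2 states that the drug can cause potentially fatal liver injury. Under Section 6.5.3.2, a case that meets its criteria, is confirmed on repeat testing and has no other explanation is reported as a serious adverse event of potential drug-induced liver injury. A site working from Table 6-4 could therefore re-expose a patient whose event the protocol elsewhere treats as reportable.

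The effect on the primary endpoint is indirect. Under Section 6.1.3 a patient discontinued for unacceptable toxicity is not counted as in sustained remission, whereas one who is interrupted and restarted may still qualify.

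**Working it through.** **Inputs.** Let b be the baseline, in multiples of ULN, of the enzyme that rises, with 1 < b <= 3.0 (the ceiling from Section 5.2). The other enzyme is taken to stay below its own limits.

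- Table 6-4 limit: T = min(3b, 5).
- Section 6.5.3.2 limit: D = max(2b, 3). The alternative of above 8 x ULN never binds, because 2b <= 6.
- Bilirubin: identical in both.

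**When is D below T?** All of these are needed: 2b < 3b (true for any b > 0), 2b < 5 (b < 2.5), 3 < 3b (b > 1) and 3 < 5 (true). So D < T exactly when 1 < b < 2.5.

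| b | D (6.5.3.2) | T (Table 6-4) | T - D | ALT/AST where only 6.5.3.2 stops |
|---|---|---|---|---|
| 1.1 | 3.0 | 3.3 | 0.3 | >3.0 to 3.3 |
| 1.5 | 3.0 | 4.5 | 1.5 | >3.0 to 4.5 |
| 1.67 | 3.33 | 5.0 | 1.67 | >3.33 to 5.0 |
| 2.0 | 4.0 | 5.0 | 1.0 | >4.0 to 5.0 |
| 2.25 | 4.5 | 5.0 | 0.5 | >4.5 to 5.0 |
| 2.5 | 5.0 | 5.0 | 0 | none |
| 3.0 | 6.0 | 5.0 | -1.0 | none (order reversed) |

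The window is widest where 3b = 5, that is b = 5/3, and the width is 5 - 10/3 = 1.67 x ULN.

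**What Table 6-4 does inside the window.** Every window lies within ALT/AST above 3.0 and up to 5.0 x ULN. The isolated enzyme row there keeps the dose unless there are symptoms or decompensation, progressively rising tests, or persistence of 4 weeks or more; any of these leads to discontinuation. Otherwise the bilirubin row decides:

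- above 2.0 to 3.0 x ULN: interrupt; resume at the same dose if resolved within 14 days, one level lower if later. If the rise is purely indirect, no dose change is required.
- above 3.0 to 10.0 x ULN: interrupt; one level lower if resolved within 14 days, discontinue if later. If purely indirect with haemolysis ruled out, reduce one level and continue at the investigator's discretion.
- above 10.0 x ULN: discontinue.

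**Example.** Baseline ALT 1.5 and bilirubin 1.0 x ULN; now ALT 4.0 and bilirubin 2.5 x ULN, cholestasis excluded.

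- Section 6.5.3.2: 4.0 > max(3.0, 3.0) = 3.0, and 2.5 > 2.0. Discontinue.
- Table 6-4: 4.0 < min(4.5, 5.0) = 4.5, so the combined row is not met. Isolated rows: ALT, keep the dose; bilirubin, interrupt, then resume at the same dose if resolved within 14 days.

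**The case against.** The arithmetic is not in dispute. The case on the other side is that the conflict is narrow and that the protocol has safeguards around it. Much of that is right.

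- **Cholestasis.** A reader might infer that every result in the window must be stopped under Section 6.5.3.2. It need not be. With ALT at 4.0 x ULN, any ALP above 2.0 x ULN gives R below 4.0/2.0 = 2 and meets the cholestasis definition. The conflict concerns non-cholestatic cases.
- **Bilirubin range.** A reader might infer opposite actions for all bilirubin values up to 10 x ULN. Table 6-4 also stops the drug for values above 3.0 x ULN unresolved after 14 days, unless the rise is purely indirect and non-haemolytic.
- **General duty to stop.** Section 10.2.1 does not point to Table 6-4 alone. The general section it also cites (9.1.1) requires discontinuation wherever participation might put the patient at risk. That permits an investigator to stop, but it rests on judgement and does not say which numerical limit governs.
- **Conservative action.** Footnote c asks for it, but its own example shows a choice between the two isolated rows. It does not bring in Section 6.5.3.2.
- **Raised bilirubin, normal enzymes.** Such a patient fits neither limb of Table 6-4's combined row, and a reader might infer a gap in cover. Section 6.5.3.2 names raised baseline bilirubin, and meeting any one of its bullets is enough, so this is not a separate error.
- **Timing.** SAP Section 1 records all 105 patients as enrolled and the primary report as final. An amendment would now change little prospectively, but that does not reconcile the two instructions.

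**Conclusion.** The inconsistency is real and should be corrected. For 1 < b < 2.5, non-cholestatic combined results between max(2b, 3) and min(3b, 5) x ULN call for a permanent stop in one section. The other gives a path to interruption and restart, and nothing ranks them.

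Its size is modest. The window is at most 1.67 x ULN wide. Except for purely indirect bilirubin rises, Table 6-4 at least interrupts the drug, so the usual dispute is over rechallenge after resolution. The conflict disappears when Table 6-4's own stop clauses apply. Few patients are likely to be affected; that is a judgement, since the documents give no rate. No analysis method, sample size or endpoint definition changes.

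It would be wrong to infer that Table 6-4 is always the laxer rule. For b above 2.5 and up to 3.0 it is the stricter one (5.0 against up to 6.0 x ULN), so neither section alone captures every required stop.

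The conclusion assumes that discontinued in Section 6.5.3.2 has its Glossary meaning. Table 6-4's separate use of interrupt and discontinue supports that reading.

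**What to change.** Leave all written thresholds as they are. Add to Section 6.5.2 and to footnote c of Table 6-4, with a cross-reference in Section 10.2.1:

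*Table 6-4 and Section 6.5.3.2 both apply to combined AST/ALT and total bilirubin elevations; if either requires discontinuation (for 6.5.3.2, after cholestasis is excluded), eltrombopag is permanently discontinued. This sentence does not limit the other criteria of Section 6.5.3.2.*

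An either-section rule is safer than naming one section as the winner. It takes the lower limit for each enzyme, so it cannot loosen any current one. Take baseline AST 1.5 and ALT 0.8 x ULN. Table 6-4 gives AST 3 x 1.5 = 4.5 and ALT 3 x 0.8 = 2.4; Section 6.5.3.2 gives 3.0 for both. Ranking either section first would raise one limit, whereas the proposed sentence gives AST 3.0 and ALT 2.4.

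No new tests are needed. The cost is possibly a few more permanent stops among patients who could have been rechallenged under Table 6-4, because its effective limit falls for 1 < b < 2.5. The documents do not show which rule the sponsor meant to prevail, so choosing the stricter result is a recommendation for the sponsor to confirm. The sentence settles combined elevations only.

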6.5.2.1 Dose modifications for other reasons

Eltrombopag dosing is to be interrupted in patients unable to ingest the drug due to mucositis or permanent vomiting.

Early discontinuation of treatment

Eltrombopag must be permanently discontinued if any of the following events occur or is identified at any time during the study:

- Cytogenetic abnormalities
 - Monosomy 7 - discontinue eltrombopag
 - Other abnormalities - discontinuation at physician discretion
- Thromboembolism, irrespective of relation to study drug
- Development of myelodysplastic syndrome or acute myeloid leukemia
- Positive pregnancy test, at any time during the study
- Difficulties in continuing eltrombopag due to AE(s)
- Patient is found to be significantly non-compliant with the requirements of the protocol (including treatment noncompliance)
- ALT of AST $> 20 \times \text{ULN}$

6.5.3 Follow-up for toxicities

Patients whose treatment is interrupted or permanently discontinued due to an AE or clinically significant laboratory value, must be followed up at least once a week (or more frequently if required by institutional practices, or if clinically indicated) for 4 weeks, and subsequently at approximately at least 4-week intervals (or more frequently if required by institutional practices, or if clinically indicated), until resolution or stabilization of the event, whichever comes first. Appropriate clinical experts such as ophthalmologist, etc. should be consulted as deemed necessary.

Patients who permanently discontinue eltrombopag for an AE or clinically significant laboratory value will be discontinued from the study and then undergo a 30-day safety follow-up.

6.5.3.1 Dose delays, modifications or discontinuation for hematologic side effects

Patients who experience a deep venous thrombosis (other than a line-related upper extremity thrombosis) or a pulmonary embolus, a transient ischemic attack or stroke, or a myocardial infarction at any time while on eltrombopag will discontinue eltrombopag.

6.5.3.2 Follow up on potential drug-induced liver injury (DILI) cases

Patients with transaminase increase combined with total bilirubin (TBIL) increase may be indicative of potential DILI, and should be considered as clinically important events.

The threshold for potential DILI may depend on the patient's baseline AST/ALT and TBIL value; patients meeting any of the following criteria will require further follow-up as outlined below:

- For patients with normal baseline ALT and AST: AST or ALT $> 3.0 \times$ ULN combined with TBIL $> 2.0 \times$ ULN OR INR > 1.5 without evidence of cholestasis (no ALP elevation)
- For patients with elevated AST or ALT or TBIL value at baseline: [AST or ALT $> 2 \times$ baseline AND $> 3.0 \times$ ULN] OR [AST or ALT $> 8.0 \times$ ULN], combined with [TBIL $> 2 \times$ baseline AND $> 2.0 \times$ ULN]
- For patients with normal baseline ALT: ALT $\geq 5 \times$ Upper Limit of Normal (ULN)

Medical review needs to ensure that liver test elevations are not caused by cholestasis, defined as Alkaline Phosphatase (ALP) elevation $> 2.0 \times$ ULN with R value < 2 in patients without bone metastasis, or elevation of ALP liver fraction in patients with bone metastasis.

Note: (The R value is calculated by dividing the ALT by the ALP, using multiples of the ULN for both values. It denotes whether the relative pattern of ALT and/or ALP elevation is due to cholestatic (R ≤ 2), hepatocellular (R ≥ 5), or mixed (R > 2 and < 5) liver injury).

These patients should be immediately discontinued from eltrombopag, and repeat liver function test (LFT) testing as soon as possible, preferably within 48 hours from the awareness of the abnormal results, then with weekly monitoring of LFTs), or more frequently if clinically indicated, until AST, ALT, or bilirubin have resolved to baseline or stabilization over 4 weeks. The evaluation should include laboratory tests, detailed history, physical assessment and the possibility of liver metastasis or new liver lesions, obstructions/compressions, etc.

1. Laboratory tests should include ALT, AST, albumin, creatinine kinase, TBIL, direct and indirect bilirubin, gamma-glutamyl-transferase (GGT), prothrombin time (PT)/ International Normalized Ratio (INR) and ALP.
2. A detailed history, including relevant information, such as review of ethanol, concomitant medications, herbal remedies, nutritional supplement consumption, history of any pre-existing liver conditions or risk factors, should be collected.
3. Further testing for acute hepatitis A, B, C or E infection and liver imaging (e.g. biliary tract) may be warranted.
4. [REDACTED]
5. Additional testing for other hepatotropic viral infection (cytomegalovirus [CMV], Epstein Barr virus [EBV] or Herpes simplex virus [HSV]), autoimmune hepatitis or liver biopsy may be considered as clinically indicated or after consultation with specialist/hepatologist.

All cases confirmed on repeat testing meeting the laboratory criteria defined above, with no other alternative cause for LFT abnormalities identified should be considered as “medically significant”, thus, met the definition of SAE and reported as SAE using the term “potential drug-induced liver injury”. All events should be followed up with the outcome clearly documented.

